Innovation. The present study extends and compliments previous yoga research. Much of the current yoga literature is limited by small sample sizes and poor methodological rigor. In response to this need, the proposed study includes a randomized controlled design, with an active control condition that is matched for time/attention, social group interactions, attention, and expectancy. It features standardized and psychometrically sound assessment instruments, including blinded evaluation, and addresses the limited generalizability of previous samples by including both men and women with broad inclusion/exclusion criteria. Finally, it is set in a Veteran population, which is an understudied group in the published literature and may differ in important ways from non-military populations. Furthermore, the yoga intervention is a manualized Hatha yoga, which has been implemented in prior studies at this facility, and is reviewed for fidelity. Thus, the proposed project addresses an important need for high quality studies of yoga for PTSD. *The greatest innovation, however, lies in the evaluation and comparison of the Attention and Coping Models. Examination of these mechanisms will advance our understanding of the way in which a guided asana practice may impact PTSD, but will also inform yoga-based mental health treatment more broadly as these transdiagnostic processes are applicable to other mental health concerns.*

Research Design and Methods

The proposed study is a randomized controlled trial of Hatha yoga as compared to supportive physical activity in Veterans with PTSD. A sample of approximately 96 recruited (refer to Sample Size). Longitudinal outcome assessment will take place over approximately a 6 month period; refer to Table 1 for an overview of measures at each time point. A 3-month follow-up is planned because information about maintenance of change following the completion of a yoga intervention is important given the long-term follow-up data from the van der Kolk trial, which suggest that ongoing practice is critical continued clinical effects (Rhodes, Spinazzola, & van der Kolk, 2016).

Procedures

Potential participants will be recruited from VA clinics (including primary care and mental health) and the community, following procedures that have been proven successful in our previous meditation and yoga trials. The initial contact for potential participants will be with a study recruiter/assessor, who will complete informed consent and conduct the evaluation for eligibility (see *Assessment*). After eligibility and consent are confirmed, the participant will complete the baseline assessment and then will have brief safety assessments every class; they will be asked to complete a total of 12 classes within 14 weeks. A follow-up will occur 12 weeks after the completion of the final class. No shows will receive a telephone follow-up. Participants will receive a payment for each assessment session (\$50 baseline part 1, \$50 baseline part 2, \$50 post-treatment part 1, \$50 post-treatment part 2, \$50 follow-up part 1, \$50 follow-up part 2 for a total of \$300; refer to Table 1).

Randomization will be done by the study statistician. In the initial phase of the trial, this was a 2:1 allocation to yoga and physical activity and took place at the individual level. Uneven allocation was planned to allow for sufficient power to accomplish the modeling proposed in Aim 2 (refer to *Sample Size*); given pandemic-related difficulties with accrual, however, the allocation will be reversed to 1:3 for the final months of the study to accomplish a minimum of 48/cell. The randomization table will be prepared prior to start of the study and revised for the new allocation strategy. Using an individual randomization strategy and continual group enrollment allows patients to begin treatment more quickly (i.e., as soon as the baseline evaluation is complete), which reduces attrition. This continual enrollment strategy is possible because the yoga and physical activity classes do not build from week to week; rather, every class provides multiple options for each pose/exercise to allow for individual differences, as is consistent with typical practice in the community. Further, sharing of personal information is minimized in this type of class, so newcomers are unlikely to cause discomfort among group members. Further, this strategy may support better retention. By allowing participants 14 weeks in which to complete 12 classes, participants will be able to make up missed classes to receive the full “dose.”

Participants. Participants will be Veterans with a diagnosis of PTSD, aged 18 or older, who are able to consent and willing to participate. Co-occurring disorders such as depression, anxiety, or treated substance abuse or dependence problems are permitted provided that PTSD is the primary presenting complaint. Heterogeneity within the group of Veterans (e.g., gender, era of service, type of trauma) is allowed for greater generalizability of the results from this sample as well as to facilitate recruitment. Trauma sensitive principles (Emerson et al., 2009) will be employed to maximize participants' comfort, particularly for individuals with concerns about personal safety/bodily integrity. The following are criteria for **exclusion**: (1) serious suicidality or homicidality that has required urgent or emergent evaluation or treatment within the past three months, (2) a known, untreated substance abuse or dependence problem (inclusion is possible if there is evidence that the individual has been afforded and is complying with treatment for the substance problem), (3) serious mental disorders, such as psychotic disorders or bipolar type I, or serious dissociative symptoms (4) cognitive impairment that would interfere with treatment, (5) circumstances that lead to recurrent traumatization (e.g., engaged in a violent relationship), (6) any medical condition for which yoga is contraindicated, including pregnancy, (7) concurrent enrollment in any other treatment specifically targeting PTSD symptoms or social functioning (e.g., couples therapy) or in any meditative or mind-body intervention (including yoga practice >1 class/month in the preceding 6 months). Participants can continue current pharmacological treatment (provided they have stabilized on medication, i.e., no additional treatment response is expected, and no changes are anticipated during the study period) or any supportive or nonspecific therapy. These selection criteria are intentionally broad so as to represent as fully as possible Veterans who may seek alternative interventions for their PTSD. The sample may have limited generalizability to non-military populations.

Assessment

Instrument selection for this trial is based on psychometric properties, past use with mental health populations and/or yoga, conceptual fit with our model and minimizing participant burden. The sample will be characterized at baseline in terms of relevant **demographic characteristics** (age, gender, race/ethnicity, relationship status, years of education, SES/income/living situation, occupation/work status, branch of service/highest rank, service connection/disability status), clinical characteristics that could affect treatment response (e.g., depression, alcohol use), and exercise tolerance (**Veterans Specific Activity Questionnaire**; Myers, Bader, Madhavan & Froelicher, 2001). The **Alcohol Use Disorders Identification Test (AUDIT**;

Babor, Biddle-Higgins, Saunders, & Monteiro, 2001) will be used to track problematic alcohol use for eligibility and clinical monitoring purposes. A score of 4 or above has excellent sensitivity for detecting current alcohol abuse or dependence (.90 and 1.0 respectively) but lower specificity (.60). At a score of 8, the specificity rises to .94 (Rumpf, Hapke, Meyer, & John, 2002). The **Life Events Checklist** portion of the PCL-5/CAPS-5 (see below) will describe the type and number of traumas to which an individual has been exposed, including identifying current circumstances that may preclude study involvement. To the extent there is heterogeneity in the sample, these data additionally may be used to explore differences in treatment response based on the nature of trauma exposure.

Eligibility. The **Montreal Cognitive Assessment (MoCA)**; Nasreddine et al., 2005) is a brief (~10 minutes) clinician-administered cognitive screening test, which will be used to screen for cognitive impairment. If the score is < 22, which has been identified as an appropriate cutoff for psychiatric patients (Gierus et al., 2015), patients will be referred for additional evaluation and excluded, unless a qualified clinician provides clearance to participate. The **PTSD Checklist – 5 (PCL-5)**; Weathers, Litz, et al., 2013) will be used to quantify PTSD symptoms; individuals with a score of 33 or greater, the currently recommended cutoff for the instrument (National Center for PTSD, 2016), will be eligible for enrollment. Individuals with lower initial PCL-5 scores will be additionally evaluated using the CAPS if they carry a clinical diagnosis of PTSD. This self-report measure of PTSD is well-established for monitoring treatment-related change and has well-documented strong psychometric properties. The PCL-5 will be repeated at each assessment point for ongoing participant safety evaluation. Given that the TBN instructors will not be mental health professionals, [name], who is a privileged and licensed clinical psychologist with specialized training and 18 years of experience in treating Veterans with PTSD, will review these data (blinded to condition) on an ongoing basis to monitor adverse reactions. Absence of serious mental illness, untreated substance dependence, serious suicidality will be evaluated using the **Mini International Neuropsychiatric Interview (MINI 7.0)**; Sheehan et al 1998), which has been validated against the SCID and CIDI. The interview takes 15-30 minutes to complete and will be supplemented with questions to assess homicidality. Finally, the participant will be queried about use of mental health services, including pharmacotherapy, psychotherapy (type, modality, frequency and duration), complementary and alternative approaches and hospitalization using the **Emory Treatment Resistance Interview for PTSD (ETRIP)**; Dunlop, Kaye, Youngner, & Rothbaum, 2014). Psychotropic medication information will be collected and cross-checked against the electronic medical record. Mental health utilization will be used to characterize the sample and also to characterize behavioral changes associated with study participation at follow-up (e.g., continued yoga or exercise).

Clinical outcomes. The **Clinician Administered PTSD Scale (CAPS-5)**; Weathers, Blake, et al., 2013) will be used to establish the PTSD diagnosis and quantify severity. This clinician-rated measure of PTSD is the “gold standard” for assessing PTSD and takes 45-60 minutes to complete. The CAPS has high internal consistency (for the DSM-IV version, alphas of 0.87 and 0.88 for the three PTSD symptom clusters and 0.95 for PTSD symptoms overall) and validity (sensitivity, specificity, efficiency, and agreement). The CAPS total score will be used as the primary measure of clinical outcome. Given our interest in exploring the effect of these interventions on symptoms that commonly co-occur with PTSD, we will also assess depression severity as measured by the 20-item **Center for Epidemiologic Studies Depression Scale Revised (CESD-R)**; Eaton, Muntaner, Smith, Tien, & Ybarra, 2004), general anxiety as measured by the 40-item **State-Trait Anxiety Inventory (STAI)**; Spielberger, Gorsuch, Lushene, Vagg, & Jacobs, 1983), anger as measured by the 35-item **State-Trait Anger Expression Inventory – II (STAXI-II)**; Spielberger, 1991) and sleep problems as measured by the 7-item **Insomnia Severity Index (ISI)**; Bastien, Vallieres, & Morin, 2001), a 7-item instrument that assesses the consequences of and distress related to insomnia, will be included as well. Finally, the **Sheehan Disability Scale (SDS)**; Sheehan, Harnett-Sheehan, & Raj, 1996), a 3-item measure of impairment in work, social and family settings, will be included. This widely-used but low-burden measure of disability has been shown to change with treatment in similar population samples (e.g., [name], Schnurr, et al., 2016).

Clinical utility. Clinical utility can be defined as the usefulness of an intervention in clinical practice and is considered to have four major dimensions (Smart, 2006). The **appropriateness** of yoga for PTSD depends on its efficacy (addressed in Aim 1) but also on the successful integration of the intervention into current care practices. **Accessibility** involves the factors involved in making yoga available to Veterans. Issues such as the usability of the manual and the way in which training can be conducted speak to **practicality**. Finally, the **acceptability** of yoga depends on its reception by key stakeholders, including Veterans and clinicians. Aspects

of clinical utility will be assessed by examining recruitment/retention data and feedback from referring clinicians and Veterans in preparation for future implementation of practice guidelines.

Mechanisms of change: Attention model. The **Philadelphia Mindfulness Scale (PMS;** Cardaciotto, [name], Forman, Moitra, & Farrow, 2008) is a 21-item measure that assesses present-moment awareness and acceptance and has good internal consistency (Cronbach's α .75) and validity (e.g., corresponds highly with other measures of mindfulness but not with measures of psychopathology or social desirability) in psychiatric samples.

To fully characterize the nature of yoga's impact on attention, we will utilize multi-modal assessment including two tasks with an affectively neutral context, as well as two tasks that include affective stimuli to allow for an assessment of the ability to deploy attentional resources in emotional contexts. The **Digit Span** test from the Wechsler Adult Intelligence Scale 4th edition (WAIS-IV) will be used as a standardized neuropsychological measure of attention and working memory (Wechsler, Coalson, & Raiford, 2008). This test includes Digit Span Forward, wherein the participant is read a sequence of numbers and recites the numbers back in the same order; Digit Span Backwards, wherein the participant is read a sequence of numbers and must recite them back in reverse order; and Digit Span Sequencing, wherein the participant is read a sequence of numbers and must recite them back in numerically ascending order. Digit Span is a well validated assessment with established norms, and has been shown to be sensitive to change in a study using a yoga intervention (Brunner et al., 2017). Each subtest is scored based on the number of items correctly recited on each trial.

Mechanisms of change: Coping model. Again, we hope to identify a latent variable indicating maladaptive coping strategies that are associated with PTSD through use of a set of indicators. The **Ruminative Thought Style Questionnaire (RTSQ)** is a 20-item, Likert-based (1-7) scale with good psychometric properties (Cronbach's α .92, strong correlations with measures of depression, anxiety and repetitive thought) and demonstrated separability from mood (Brinker & Dozois, 2009). The **Emotion Regulation Questionnaire (ERQ;** Gross & John, 2003) is a 10-item measure of reappraisal and expressive suppression, which are thought to be effective and ineffective emotion regulation strategies respectively. The ERQ expressive suppression subscale has previously been shown to be impacted by yoga in PTSD patients (Dick et al., 2014) and has good convergent and discriminant validity and internal consistency (Gross & John, 2003). Experiential avoidance will be quantified using the **Brief Experiential Avoidance Questionnaire (BEAQ;** Gamez et al., 2014). This 15-item Likert-based (1-6) measure was developed to improve on the Acceptance and Action Questionnaire – II (AAQ-II), which has been shown to be highly reflective of general distress (Wolgast, 2014). The BEAQ has good internal consistency (Cronbach's α .86) and is more strongly related to measures of avoidance than negative affect.

To assess the construct of tolerance of discomfort, we will use the **Distress Tolerance Scale (DTS),** a 15-item, Likert-based (1-5) scale with good internal consistency (Cronbach's α .75) and test-retest reliability ($r = .61$). The DTS has been shown to be associated with PTSD (Vujanovic et al., 2013), prospectively predict problematic alcohol use (Simons & Gaher, 2005) and be modified by hatha yoga (Medina et al., 2015).

Assessment schedule. The assessment schedule presented in Table 1 is designed to balance depth of understanding with participant burden. Constructs with a greater degree of fluctuation (e.g., mental health symptoms) are administered more frequently, whereas those that change more slowly are assessed less frequently (e.g., functioning).

Table 1: Summary of Assessments

	Instrument	Aim	Baseline	Weekly	Mid-treatment	Post-treatment	Follow-up	Assessment session
Descriptives, Eligibility, Covariates	Demographics		X					1
	Veterans Specific Activity Questionnaire		X					1
	Alcohol Use Disorders Identification Test		X	X	X	X	X	1
	Life Events Checklist		X					1
	HRV		X			X	X	2
	Montreal Cognitive Assessment		X					1
	PTSD Checklist-5		X	X	X	X	X	1
	Mini International Neuropsychiatric Interview		X					1
	Emory Treatment Resistance Interview for PTSD		X			X	X	1
Clinical Outcomes	Clinician Administered PTSD Scale 5	1a	X			X	X	1
	Center for Epidemiologic Studies Depression Scale	1b	X	X	X	X	X	1
	State-Trait Anxiety Inventory	1b	X		X State only	X	X	1
	State-Trait Anger Expression Inventory	1b	X		X	X	X	1
	Insomnia Severity Index	1b	X		X	X	X	1
	Sheehan Disability Scale	1b	X		X	X	X	1
Mechanisms of Change	Attention Model							
	Philadelphia Mindfulness Scale	2a	X			X	X	1
	Digit Span	2a	X			X	X	2
	Coping Model							
	Ruminative Thought Style Questionnaire	2b	X			X	X	1
	Emotion Regulation Questionnaire	2b	X			X	X	1
	Brief Experiential Avoidance Questionnaire	2b	X			X	X	1
Distress Tolerance Scale	2b	X			X	X	1	

Intervention

Yoga. The proposed yoga program is a classical Hatha practice, which is currently used at the VA San Diego. Hatha yoga refers to practice of physical asanas, or poses, as opposed to practices that are limited to breath-work or are primarily meditative. The program is designed to minimize the risk of injury and make the poses accessible to a wide range of people (Iyengar, 1979). The manualized program (see the manual and

home practice guide presented in the *Appendix*) includes 23 asanas (32 total variations), which are conducted at a slow-moderate pace in the context of a positive intention. Asanas are aligned with the breath, and the instructor describes/demonstrates optimal alignment. In addition, participants are encouraged to focus on an intention (a goal or positive direction for their yoga practice). Sessions are structured as follows: breath-based meditation (5 minutes), basic postures to warm-up the body (Poses 1-8; 10 minutes), standing poses (Poses 9-14; 15 minutes), floor poses (Poses 15-22; 15 minutes), “savasana” (i.e., complete relaxation; 10 minutes). The manual contains pictures and a description of how to perform each pose with typical instructor dialogue to maximize consistency across instructors. Participants are cautioned to stop if any pose becomes painful (as opposed to uncomfortable) and to consult with the instructor individually about any problems that arise. Although this program has not been specifically applied to PTSD, we selected it because it employs commonly used asanas, has been successfully applied at this facility, is known to be safe, and impacts mental health. In addition, it requires no specialized training beyond basic yoga certification so would be easily disseminable. *There is no current empirical basis for the selection of any particular practice type or asanas for the treatment of PTSD; this project would provide such guidance.*

The 12-class program will be delivered in one 60-minute yoga class/week for 12-14 consecutive weeks with at home practice of 15-20 minutes/day. This frequency/length of intervention was chosen because it is similar to other PTSD interventions (e.g., CPT; Voelkel, Pukay-Martin, Walter, & Chard, 2015) and similar to the “dose” in successful yoga clinical trials, e.g., 8 90-minute sessions Jindani et al., 2015) or 10 60-minute sessions (van der Kolk et al., 2014). The importance of attending all sessions and practicing between sessions is stressed throughout. Text reminders will be sent before all classes, a strategy which has had a positive effect on attendance in our current compassion meditation trial. Participants who miss a session without notifying the instructor will be contacted to check on the reason for non-attendance and to encourage them to resume participation as soon as possible. Fidelity to the manual will be assessed using video recordings of sessions. All yoga sessions will be video-recorded with instructor/participant consent. Ten percent of the sessions will be randomly selected for review by an independent certified yoga instructor. Sessions will be rated using an adherence checklist for each procedure or instruction.

The instructor will be certified (minimum of RYT-200; Yoga Alliance, 2016) and trained in trauma-sensitive yoga principles, which is a set of adaptations to enhance the comfort of trauma survivors. Trauma-sensitive practice involves using invitational (as opposed to commanding) language, providing a space where clients feel less vulnerable (e.g., lighting should not be too dark), allowing patients to opt out of postures, minimizing physical assists until trust is established, and creating an overall welcoming and approachable environment (Emerson et al., 2009).

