Thus, the successful track record of implementing clinical and research programs using complementary approaches at the VASDHS, is strong evidence for the acceptability of this type of study at this facility.

Feasibility

Although we initially projected being able to enroll approximately 6 Veterans per month in the trial for a sample of 144 completers, this has not proven to be realistic. In 38 months of active recruitment, we have screened 326 individuals (~9/month) of whom 51% consented to participation and 26% were randomized (~2.5/month). We believe that these lower-than expected rates of participation and randomization are partly related to competition with many other opportunities to engage in recorded or live-streamed yoga/exercise classes. As a result, we plan to enroll approximately 96 Veterans in the trial (48/group).

Pilot Effect Sizes

Effect sizes in studies of yoga for PTSD vary widely (0.08 to 1.65; Wells, [name], Schmalzl, Groessl, & Strauss, 2016), perhaps because of variability in practice types and the populations studied. The largest randomized controlled trial of yoga for PTSD to date compared a “trauma sensitive” version of Kundalini yoga to a wait list control in an 80-person civilian sample (Jindani et al., 2015). Greater decreases in PTSD symptoms (Cohen’s $d = 1.65$), insomnia, stress and anxiety were observed in the yoga group. In addition, yoga was associated with increased in positive affect and resilience. No significant changes in depression or negative affect were observed. This trial is limited, however, by the lack of an active control and a high rate of

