conditioning. Each exercise can be modified to meet the needs of individual participants. The classes will be conducted by certified personal trainers. This control group was selected because of its past use as a control condition for Hatha yoga. This type of exercise program was comparable to Hatha yoga in terms of gains in functional fitness (Gothe & McAuley, 2016) but less effective at improving cognition (Gothe, Kramer, & McAuley, 2014) in community-dwelling samples of older adults.

Analytic Plan

Descriptive statistics will be obtained for all variables, including distributions, means, medians, variances, standard deviations, skewness, kurtosis, ranges, and quartiles. Tests of normality of continuous measures will be made using the Shapiro-Wilk W and the Kolomogorov D statistics in conjunction with plots of the distribution of data and descriptive measurements. The data will also be examined for homogeneity of variance. An appropriate statistical method will be employed to correct for any abnormalities. Missing data values will be minimized by intensive training of the assessors in techniques of clarifying answers and checking questionnaires while participants are on-site. When missing values are identified, we will employ several approaches to reduce their influences. If at all possible, participants will be rescheduled or a telephone call will be made within 24 hours of completion of tests or interviews. The pattern of missing data will be examined according to the procedure recommended by Little and Rubin (1987), which includes comparing group differences in the primary outcomes of subjects with versus without missing data. We will also test whether the drop-outs are random or systematic by comparing the drop-outs with the study completers on the baseline data. An absence of significant differences would support the random nature of drop-outs. Effect of drop-outs will be minimized by including all subjects in the analyses and by including any effect of systematic differences between the drop-outs and completers in the model as a covariate when applicable.

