Each outcome variable will be graphed versus time for each subject for all available time points (baseline, mid-treatment, post-treatment, follow-up) to evaluate what function of time best describes the data. Hypotheses 1a and 1b will be tested using the Mixed Effect Model (Hedeker, Gibbons, & Waternaux, 1999). This method is robust with respect to drop-out and missing data. These mixed models allow us to assess whether important estimates are dependent on missing data patterns, and provide overall estimates of effects by averaging over the various missing-data patterns (Hedeker et al., 1999). In addition, we will use the extension of the Pattern-Mixture Models (Guo, Ratcliffe and Ten Have, 2004), which allows subject-to-subject heterogeneity and assess if there is bias due to drop out or missing data. The Mixed Effect method has several advantages over more traditional analytic approaches such as a change score, end-point or repeated measures analysis of variance. It allows the inclusion of subjects with missing data or those who were terminated early in the study, without relying on data imputation procedures. This method provides an estimate of the individual variability around the population trend, the variability of the individual intercepts (baseline values) and slopes (changes across time), and the correlation between them. We will include a random intercept, a random effect for assessment time, and fixed effects for comparison groups and group-by-time interaction in the model. A fully saturated treatment by time model will be utilized for inference. Co-variance structure will be chosen based on Akaike's Information Criterion (AIC). Random group level treatment effects will also be evaluated for importance based on the model AIC. This allows for any group level effects to be incorporated into the model. Denominator degrees of freedom will be calculated using the Kenward-Roger small sample correction. Statistical significance will be determined by $p < .05$ for hypothesis 1a and $p < .01$ (.05/5 to correct for multiple comparisons) for hypothesis 1b.

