Sample size. We used the method provided by Hedeker, Gibbons, & Waternaux (1999) for the Random Regression Model and the RMASS program provided by Hedeker (2016) to estimate needed sample size for Aim 1. Medium effect size was selected based on finding from previous yoga trials (Wells et al., 2016) and was defined as a between-group difference increasing linearly from 0 at baseline to .5 SD units at the last time point. The minimum power estimation is based on sample size calculation for 10% and 20% attrition, correlations of 0.2, 0.5, and 0.8 between the repeated measures, and for medium and large effect sizes. We are confident that with the proposed total sample size of at least 48/arm would be sufficient to achieve a minimum 80% power for the primary aim.

Management

Management of this single-site study will be [name] responsibility. She has considerable experience in research management from small developmental grants (e.g., NCCIH R34) to a large multi-site consortium (INTRuST PTSD/TBI Clinical Consortium Deputy Director) and center of excellence (VASDHS CESAMH Associate Director). Administrative aspects of the project will be supported by [name], who has been [name] lead coordinator for more than a decade. [name] will coordinate scientific aspects of the project, holding regular meetings with the investigative team. [name], the study biostatistician, will work closely with [name] around data management and analysis. [name] will draw on his experience with yoga research to help with issues of recruitment, enrollment and retention. Drs. [name] (attention) and [name] (pain) will provide guidance in their relative areas of expertise. [name], who is a licensed clinical psychologist, also will be responsible for clinical oversight. The timeline of major study activities is presented in Table 2.

Table 2. Study Timeline

Year 1 (2018-2019)	Year 2 (2019-2020)	Year 3 (2020-2021)	Year 4 (2021-2022)	Year 5 (2022-2023)
Original Timeline				

Set-up	Recruitment (approx. 6/month x 30 mos)	Follow-up, data lock	Dissemination	Analyses	
Regulatory	Assessment				
Hiring	Intervention delivery, fidelity (12 groups)				
Training	Data management				
Recruitment	DSMB reporting				
Revised Timeline					

 ✓ Set-up ✓ Regulatory 	
 Recruitment (approx. 6/month x 30 mos) Assessment Intervention delivery, fidelity (12 groups) Data management DSMB reporting 	Follow-up, data lock	Dissemination	Analyses	

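### The allocation ratio moves from 2:1 to 1:3 for the final months, but the primary model has no allocation-phase term, so part of any phase difference in CAPS-5 change enters the arm contrast

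*Combined protocol and SAP*

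**What the plan says.** On allocation (Research Design and Methods, Procedures): "In the initial phase of the trial, this was a 2:1 allocation to yoga and physical activity and took place at the individual level". After accrual fell short, "the allocation will be reversed to 1:3 for the final months of the study to accomplish a minimum of 48/cell". The randomisation table is to be revised for the new ratio. The section says nothing about the analysis of the two periods.

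On the primary analysis (Analytic Plan): Hypothesis 1a is tested with a mixed model that has a random intercept, a random time effect and "fixed effects for comparison groups and group-by-time interaction in the model". A saturated treatment-by-time model is used for inference. Random group-level effects are kept or dropped on AIC. The only route for covariates is "including any effect of systematic differences between the drop-outs and completers in the model as a covariate when applicable".

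On numbers (Feasibility): 326 people were screened in 38 months and 26% were randomised, described as about 2.5 a month. The revised target is about 96, or 48 per group.

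**The concern.** Randomisation protects the comparison within each phase. It does not protect a comparison pooled over phases with different ratios unless the analysis respects the phase. People who enter late are mostly in the control arm, and people who enter early are mostly in yoga. If late entrants change more or less on CAPS-5 than early entrants, for any reason, yoga is penalised or credited for part of that difference.

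Nothing in the plan closes the gap:

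- Saturating treatment by time saturates arm and visit, not phase.
- The covariate rule concerns drop-outs versus completers.
- The AIC-selected group effects represent class groups and may be dropped.
- Subject-level random effects do not remove a systematic difference that is associated with arm.

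The confounding is partial, because both arms are randomised in each phase. It concerns change only: a phase difference in baseline level cancels from the group-by-time contrast. The documents do not show that the phases differ in change. They do give a reason not to assume equality, since the 2022 timeline (Management, Table 2) has recruitment moving from in person to remote. The ratio switch is not dated against that move.

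**Working it through.** **Inputs from the documents.** Ratios 2:1 then 1:3; target 96 (48/48), with a minimum of 48 per cell; 326 screened and 26% randomised over 38 months; two-sided alpha 0.05; 10% and 20% attrition considered in Sample size.

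**Assumed.** The realised split by phase is not given, so five scenarios are used. The phase difference D is set at 0.1, 0.3 and 0.5 SD of change. The SD of change equals the raw SD at a correlation of 0.5.

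**The plan's own figures.** 0.26 × 326 = 84.8 randomised, or 84.8/38 = 2.2 a month. The stated 2.5 a month gives 2.5 × 38 = 95. Both counts are carried forward. The 80% minimum power in Sample size was not reproduced for its medium effect. A linear slope test at 48 per arm with three CAPS-5 visits and 10 to 20% attrition gives 44–47%, 62–66% and 94–96% at correlations 0.2, 0.5 and 0.8. That is a separate point, and nothing below depends on it.

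**Formulas.** With n1 people at 2:1 and n2 at 1:3:

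- Yoga Y = 2n1/3 + n2/4; control C = n1/3 + 3n2/4.
- Imbalance L = (3n2/4)/C − (n2/4)/Y, the late-phase share of control minus that of yoga.
- Bias (absolute) = L × D; SE = √(1/Y + 1/C), in SD of change.
- Type I error = P(|Z + bias/SE| > 1.96).
- Variance ratio, adjusted to unadjusted = [YC/(Y+C)] / Σ[y·c/(y+c)], summed over the two phases.

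**Worked case, exactly 48/48.** Solving 2n1/3 + n2/4 = 48 with n1 + n2 = 96 gives n1 = 57.6 (38.4 yoga, 19.2 control) and n2 = 38.4 (9.6 yoga, 28.8 control). Then L = 28.8/48 − 9.6/48 = 0.60 − 0.20 = 0.40 and SE = √(2/48) = 0.204. At D = 0.3 the bias is 0.12, bias/SE = 0.59 and type I error is 9.0%. The variance ratio is 24/(12.8 + 7.2) = 1.20, an effective N of 96/1.20 = 80.

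| Scenario | Total (Y/C) | Late share, Y vs C | L (points) | Bias at D = 0.1 / 0.3 / 0.5 | Type I error, % | Variance ratio |
|---|---|---|---|---|---|---|
| A. Exactly 48/48 | 96 (48/48) | 20.0% vs 60.0% | 40 | 0.04 / 0.12 / 0.20 | 5.4 / 9.0 / 16.5 | 1.20 |
| B. 85 at 2:1, then 1:3 until C = 48 | 111 (63.1/48) | 10.4% vs 41.1% | 31 | 0.03 / 0.09 / 0.15 | 5.3 / 7.7 / 12.6 | 1.15 |
| C. 95 at 2:1, then 1:3 until C = 48 | 117 (68.8/48) | 7.9% vs 34.0% | 26 | 0.03 / 0.08 / 0.13 | 5.2 / 7.0 / 10.7 | 1.12 |
| D. 85 at 2:1, stop at 96 | 96 (59.3/36.7) | 4.7% vs 23.0% | 18 | 0.02 / 0.05 / 0.09 | 5.1 / 5.8 / 7.2 | 1.08 |
| E. 95 at 2:1, stop at 96 | 96 (63.6/32.4) | 0.4% vs 2.3% | 2 | 0.00 / 0.01 / 0.01 | 5.0 / 5.0 / 5.0 | 1.01 |

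With 20% attrition, A becomes 5.4 / 8.2 / 14.2% and B becomes 5.2 / 7.1 / 11.1%.

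**Simulation check.** Integer counts were 38/19 early and 10/29 late, with 20,000 runs of a linear model on change. Without a phase term, type I error at D = 0.1 / 0.3 / 0.5 is 5.4 / 8.5 / 15.1%; with it, 5.0 / 4.9 / 4.9%. The unadjusted figures fall slightly below the formula because the omitted phase effect inflates the residual variance. A saturated mixed model with three CAPS-5 visits (300 runs, D = 0.3) gave a yoga-minus-control bias of −0.12 without phase terms and about 0 with them.

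**The case against.** **The worst case fits the accrual figures poorly.** Scenario A needs only about 58 people at 2:1, yet about 85 seem already to have been randomised and the ratio change is written in the future tense. At 2:1, 84.8 people give 56.5 in yoga, so 48 controls would need at least 56.5 + 48 = 104.5 in total, which is more than 96. This stands. A is what the stated 48/48 in 96 implies, but it is reachable only if the reported count already includes people randomised at 1:3. On the plain reading the imbalance is at most about 31 points. The milder scenarios D and E, however, leave about 37 and 32 controls and miss the plan's minimum of 48 per cell. Meeting that minimum from 85 to 95 early entrants gives 26 to 31 points.

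**The phase difference is undocumented.** This also stands. At 0.1 SD the type I error never exceeds 5.4%, and the 0.5 SD column assumes a phase difference as large as the planned treatment effect.

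**Adjustment can cost accuracy.** Squared bias equals the added variance at D = √(SE²adj − SE²)/L, which is 0.23 SD in A, 0.24 in B and 0.33 in D. Below those values the unadjusted estimate has the smaller mean squared error. That is correct, but the unadjusted test holds its level only if the phases do not differ, which the plan neither states nor justifies. Analysing by the strata actually randomised is the safer default in a confirmatory comparison.

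**The figures come from a pre-post contrast.** The mixed-model check confirms the bias but is too small to give type I error. No calculation was made for the mediation models.

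**Conclusion.** The concern holds. Entry phase is tied to arm by design, and no planned term accounts for it. That follows from the text and needs no assumption.

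The size is conditional. It rests on the assumed split by phase, an assumed phase difference of 0.1 to 0.5 SD of change, and a simple pre-post contrast at a correlation of 0.5. If the 48-per-cell minimum is met, 26 to 40% of any phase difference enters the arm contrast. Type I error is then 5.2 to 5.4% at 0.1 SD, 7.0 to 9.0% at 0.3 SD and 10.7 to 16.5% at 0.5 SD. If recruitment stops at 96 after 85 or more early entrants, it is at most 7.2%. The harm therefore runs from none to material, and its direction cannot be known in advance. Because the ratio change is planned, the adjustment can and should be fixed before outcomes are analysed.

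**What to change.** Before outcomes are analysed, add one sentence to the Analytic Plan: the primary model, and the other models that compare arms, include a fixed effect for allocation phase (2:1 versus 1:3) and its interaction with visit. The treatment contrast is then a within-phase comparison pooled over phases. Report the number randomised to each arm in each phase. Label any phase-specific estimates as descriptive, since the late phase may hold only about 3 to 10 yoga participants, or fewer if the switch comes very late.

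No new data are needed. The cost is precision. If the phases truly do not differ, the standard error rises by about 10% in scenario A, 7% in B, 6% in C, 4% in D and under 1% in E. At 48/48 with 20% attrition, power of the simple pre-post contrast for 0.5 SD of change falls from about 0.59 to 0.52. The unadjusted analysis can be kept as a pre-specified sensitivity analysis.
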